Note: In patients in whom there is no known history of thyroid disease and who are not on thyroid hormone replacement medication, if TSH is up to 1.5 x ULN at Screening with normal free T4, 1 repeat test is allowed to confirm the elevation in TSH. If TSH and free T4 are normal upon repeat testing and there is no clinical suspicion of thyroid disease or history of elevated TSH, the patient may be included. All thyroid axis testing should be performed in the morning, approximately at the same time.

- 8. Total bilirubin > 1.2 mg/dL
- 9. Albumin < 3.5 g/dL
- 10. INR > 1.2 in patients who are not on anticoagulant therapy
- 11. ALT or AST > $5 \times ULN$
- 12. Unstable elevated ALT or AST: Patients with ALT or AST > 60 IU/L must have evidence of a stable value over at least a 2-week time period prior to randomization as evidenced by one of the following:
 - a. Comparison to a historical value, if available, obtained within 2 to 12 weeks prior to the Screening visit: Screening value must be $\leq 30\%$ higher than a documented historical value (Note: the historical value must be $\leq 5 \times ULN$)

OR

b. Repeat value at least 2 weeks after the Screening value: Repeat value should be $\leq 30\%$ higher than the value from the Screening visit, and the repeat value must be $\leq 5 \times \text{ULN}$ (Note: repeat only the analyte(s) that is/are > 60 IU/L at Screening)

Note: If the Investigator has clinical suspicion for acute liver injury in a patient for other reasons, the patient should be excluded after discussion with the Medical Monitor.

Note: The MRI-PDFF and cT1 may proceed on the basis of the initial ALT value at Screening, given all other eligibility criteria are met, but randomization should not occur prior to confirmation of ALT and/or AST stability as specified above.

- 13. ALP > 1.5 x ULN
- 14. Platelet count < 150,000 /mm³
- 15. $eGFR < 60 \text{ mL/min}/1.73 \text{m}^2$ (Refer to Appendix 5 for the eGFR formula)
- 16. Weight loss of > 5% total body weight within 3 months prior to Screening
- 17. History of a malignancy within 2 years of screening, with the following exceptions:

CONFIDENTIAL

- a. Adequately treated carcinoma in situ of the cervix
- b. Adequately treated basal or squamous cell cancer or other localized non-melanoma skin cancer
- 18. Prior or planned (during the study period) bariatric surgery (e.g., gastroplasty, roux-en-Y gastric bypass)
- 19. Type 1 diabetes

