2.1.4. Treatment Assignment, Blinding, and Randomization Methodology

Patients will be randomized to study drug or placebo using an Interactive Web Response System (IWRS). Approximately 140 patients will be randomized at an overall ratio of 1:1:1:1:1:1:1 into the 7 groups treatment groups as described in Table 2.

Investigators, patients, all study personnel, and the Sponsor will remain blinded to each patient's assigned dose group throughout the course of the study. The randomization codes will be provided to bioanalytics to allow for the exclusion of placebo patients from the PK assay.

Randomization codes will remain blinded until the trial is officially unblinded.

Emergency unblinding procedures are outlined in Section 6.4.1 of the study protocol and in the unblinding plan. Additional unblinding will be reviewed in the medical monitor plan (Maintaining Study Blind and Unblinding Plan).

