- Antithrombotic medications defined by WHODD SDG of "Antithrombotic drugs"
- Antidiabetic medications defined by the WHODD SDG of "Drugs used in diabetes"
- Hormonal contraceptives defined by the WHODD SDG of "Drugs used in Hormonal contraception"
- Vitamin E defined by the WHODD drug codes beginning in "001105" or if "VITAMIN E" is found in the preferred drug name
- Pioglitazone or other PPARγ agonists defined by WHODD ATC level 4 A10BD and A10BG
- o GLP-1 analogues defined by WHODD ATC level 4 code (term) A10BJ (Glucagon-like peptide-1 [GLP-1] analogues)
- DPP-4 inhibitors defined by WHODD ATC level 4 code (term) A10BH (Dipeptidyl peptidase 4 [DPP-4] inhibitors)
- SGLT2 inhibitors defined by WHODD ATC level 4 code (term) A10BK (Sodium-glucose co-transporter 2 [SGLT2] inhibitors)

The following baseline laboratory tests will be summarized as continuous variables and as frequencies for categorizations described:

- Baseline ALT level (U/L):
 - $\circ \le 60 \text{ U/L versus} > 60 \text{ U/L (overall and by sex)}$
 - < 2x ULN versus $\ge 2x$ ULN to < 5x ULN
- Baseline AST level (U/L): The same subgroups as specified for ALT above will be used
- Baseline GGT level (U/L): $\leq ULN$, > ULN
- Baseline ALP level (U/L): $\leq ULN$, > ULN
- Baseline total bilirubin level (mg/dL)
- Baseline fasting HDL cholesterol (mg/dL)
- Baseline fasting LDL cholesterol (mg/dL)

CONFIDENTIAL

- Baseline fasting total cholesterol (mg/dL)
- Baseline fasting triglycerides (mg/dL)
- Baseline fasting glucose level (mg/dL)
- HbA1c (%): $< 6.5\%, \ge 6.5\%$
- Baseline platelet count $(10^9/L)$:
- Baseline free T3 (FT3)
- Baseline total T3
- Baseline free T4
- Baseline total T4
- Baseline TBG
- Baseline rT3
- Baseline FT3/rT3

Demographics and baseline characteristics will be summarized by treatment group and overall, for the Safety, Efficacy, and Per Protocol Analysis Sets.

All demographic and baseline characteristics data will be presented in by-patient data listings.

No inferential statistical comparisons will be performed.

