7.4. Multicenter Studies

The randomization is not stratified by site. Likewise, analyses of data will not be stratified by study site.

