8.3.5. Shifts in Normal Range

Shift tables for each laboratory test (hematology, chemistry, and urinalysis) showing the shift from normal at baseline to abnormal at each post-baseline visit will be presented by visit. Summaries will present the number and percentage of patients with shifts by treatment group. Denominators for percentages will be the number of patients with non-missing data at the specific assessment and baseline.

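### SAP 8.3.5 laboratory shift percentages count only normal-to-abnormal shifts but divide by all evaluable patients, so they understate the risk among patients who can shift and move with baseline mix

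*SAP*

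**What the plan says.** SAP section 8.3.5 (Shifts in Normal Range) plans shift tables for every hematology, chemistry and urinalysis test. Only one direction is described, "showing the shift from normal at baseline to abnormal at each post-baseline visit", with counts and percentages by treatment group and visit. The denominator rule follows: "Denominators for percentages will be the number of patients with non-missing data at the specific assessment and baseline." It does not restrict the denominator to patients who were normal at baseline.

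Other parts of the documents show that abnormal baselines are expected on several of these tests:

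- **ALT and AST.** Protocol section 5.2 excludes only values above 5 x ULN and sets a stability rule for raised values: "Patients with ALT or AST > 60 IU/L must have evidence of a stable value over at least a 2-week time period prior to randomization."
- **ALP.** Protocol section 5.2 excludes only values above 1.5 x ULN.
- **GGT.** Protocol section 5.2 sets no limit. SAP section 6.2 tabulates baseline GGT and ALP as at or below ULN versus above ULN.
- **eGFR.** It is listed under clinical chemistry in Protocol Appendix 1. Protocol section 5.2 excludes only values below 60, while SAP section 8.3.1 defines normal as 90 or above.

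On arm size, SAP section 2.1.4 states: "Approximately 140 patients will be randomized at an overall ratio of 1:1:1:1:1:1:1." That is about 20 per arm. SAP section 7.4 adds: "The randomization is not stratified by site." No stratification by baseline laboratory status is described.

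**The concern.** The numerator and the denominator describe different groups. Only patients with a normal baseline can make the tabulated shift, yet the percentage is taken over everyone with paired data.

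Two consequences follow for a test with a sizeable baseline-abnormal share. First, the percentage is not the risk of becoming abnormal; it is that risk scaled down. Second, the scaling factor belongs to the arm. Two arms with the same risk print different percentages if their baseline mix differs, and in arms of about 20 some difference is likely. A reader comparing columns could take baseline mix for a dose pattern, or could see a real difference reduced.

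**Working it through.** The documents state no shift percentage, so there is no figure to reproduce. The check is algebra, followed by illustrations under stated assumptions.

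**Definitions, for one test, arm and visit**

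- N = patients with both a baseline and a visit value (the SAP denominator)
- N0 = those of the N who were normal at baseline
- x = those of the N0 who are abnormal at the visit (the SAP numerator)
- f = N0/N, the share normal at baseline

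**Identity**

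SAP percentage = x/N = (x/N0) x (N0/N) = at-risk percentage x f.

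The two percentages agree only when f = 1 or x = 0. If two arms have the same f, their ratio is preserved and their absolute difference shrinks by the factor f. If f differs, the ratio is distorted as well.

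**Size of the understatement**

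The documents do not give f, so I assume a range. With an assumed at-risk rate of 25%:

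| f (assumed) | SAP percentage = 25% x f | At-risk percentage |
|---|---|---|
| 0.3 | 7.5% | 25% |
| 0.5 | 12.5% | 25% |
| 0.7 | 17.5% | 25% |
| 0.9 | 22.5% | 25% |

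**Equal risk, different baseline mix (20 per arm, all with paired data)**

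| Normal at baseline | Shifts at 25% | SAP prints | At-risk |
|---|---|---|---|
| 8 | 2 | 2/20 = 10% | 2/8 = 25% |
| 12 | 3 | 3/20 = 15% | 3/12 = 25% |
| 16 | 4 | 4/20 = 20% | 4/16 = 25% |

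**How often chance alone produces such imbalance**

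Treat the number normal at baseline in each arm as an independent Binomial(20, f) count. For a given pair of arms, sum the joint probabilities over the stated gap. The last column is the simulated mean of the largest minus the smallest of seven such counts, divided by 20.

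| f (assumed) | Pair differs at all | Pair differs by 4 or more of 20 | Expected range of the share over 7 arms |
|---|---|---|---|
| 0.3 | 0.86 | 0.23 | 27 points |
| 0.5 | 0.87 | 0.27 | 30 points |
| 0.7 | 0.86 | 0.23 | 27 points |
| 0.9 | 0.79 | 0.06 | 17 points |

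Neighbouring rows of the equal-risk table differ by 4 of 20, which is an ordinary imbalance for f between 0.3 and 0.7. The outer rows differ by 8 of 20. For a given pair, a gap of 8 or more has probability 0.017 at f = 0.5 and 0.009 at f = 0.3 or 0.7. With seven arms, some pair is more likely to show it.

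**The case against.** The strongest reply is that nothing is miscalculated. The SAP states its denominator openly, and the share of all evaluable patients who newly became abnormal is a legitimate descriptive quantity. It is too low only when read as a risk among patients who could shift, which section 8.3.5 does not claim. That stands. What remains is that a table showing only shifts out of normal invites the at-risk reading, and its columns are not comparable when baseline mix differs.

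A reader might infer that the trial's liver-safety rates in general are understated. The documents do not support this. SAP section 8.3.1 reports CTCAE increases of at least 1 and at least 2 grades by test. Its Table 11 reports ALT/AST, bilirubin and ALP in multiples of ULN, with a listing of every patient who meets a criterion. SAP section 8.3 summarizes change and percent change by visit, and section 7.9 applies ANCOVA to change in ALT, AST and GGT. None of these uses the 8.3.5 denominator. They do not fully replace the shift table, however: Table 11 starts at 3 x ULN for ALT/AST and 2 x ULN for ALP, and it omits GGT.

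A reader might also infer a large, known bias. The documents give no baseline-abnormal share. SAP section 6.2 splits ALT and AST at 60 U/L and 2 x ULN, not at ULN, so even that table will not show how many patients start abnormal on them. It will show the mix for GGT and ALP by arm, which partly mitigates the problem for those two tests.

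The effect is not uniform across tests. Entry limits on total bilirubin, albumin and platelets mean few patients should start abnormal in the direction of concern, so the two denominators should nearly coincide there. Finally, the table shells are not available here, and they may already print the baseline-normal count.

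**Conclusion.** The point holds as a reporting flaw in one descriptive safety table. The 8.3.5 percentage equals the at-risk percentage times the share normal at baseline. It therefore understates the risk among patients who can shift, and it can vary between arms of about 20 through chance baseline mix. The tests most exposed are ALT, AST, GGT, ALP and eGFR. Including eGFR assumes that the normal range set in SAP section 8.3.1 also applies in 8.3.5; the SAP gives no other.

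The algebra needs no assumption. The size does: the 25% risk and the values of f are illustrative, and the imbalance probabilities assume independent binomial counts with all 20 patients evaluable. Imbalance is likely but not certain for any one test.

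No hypothesis, efficacy endpoint or stopping rule depends on this table, and the other liver-safety outputs are unaffected. I rate it minor to moderate, worth correcting because the correction is cheap.

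**What to change.** In SAP section 8.3.5, define the denominator as patients with a normal baseline value for that test and a non-missing value at that visit, and print that n beside each percentage. Alternatively, present the full baseline-by-visit table (low, normal, high) with row percentages. This shows the same at-risk figures and also the movement of patients who began abnormal.

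Either option needs a one-sentence SAP change and an edit to the table program, with no new data. The downside is smaller denominators and less precise percentages. For example, the exact (Clopper-Pearson) 95% interval for 4/8 runs from 16% to 84%. Printing the n makes this visible, and the table should remain descriptive.

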8.4. Vital Signs

Vital signs will be collected at each visit. Summary statistics will be provided for systolic and diastolic blood pressure, and heart rate for each visit. Any clinically significant abnormalities will be reported as adverse events.

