1.2. Schema

1.3. Schedule of Activities (SoA)

	Screening]	Freatmen	t Period ^f			Follow -Up ^b	ET ^a	Notes
Visit	Screening	Week 0	Week 2	Week 4	Week 6	Week 8	Week 12	Week 16		
Study Day		Day 1	15	29	43	57	85	113		
Schedule Window (days)	-42 days		± 3	± 3	± 3	± 3	± 3	-7 /+2		Patients discontinuing the study at any time for any reason (Early Termination) should complete the ET visit as soon as feasible and return for a Follow-Up visit 4 weeks (-7 days /+2 days) after the last dose of study drug.
Clinical Procedure	s/Assessmen	its								
Written Informed Consent	х									Written informed consent may be obtained via telephone in accordance with Section 10.1.2. Screening may be initiated via telephone to avoid a visit to the site, if the patient is disqualified based on medical history.
Demographics	Х									Includes age (year of birth), sex, race, and ethnicity.
Weight	Х	х			Х		X	х	х	
BMI	Х									
Height	Х									
Medical history	х									Medical history including details of illnesses, allergies, or procedures including liver biopsy, date(s) of onset, whether condition(s) is currently ongoing, medication history, including alcohol use
Complete Physical Examination	х							Х	х	

	Screening		1	Freatmen	t Period ^f			Follow -Up ^b	ET ^a	Notes
Visit	Screening	Week 0	Week 2	Week 4	Week 6	Week 8	Week 12	Week 16		
Study Day		Day 1	15	29	43	57	85	113		
Schedule Window (days)	-42 days		± 3	± 3	± 3	± 3	± 3	-7 /+2		Patients discontinuing the study at any time for any reason (Early Termination) should complete the ET visit as soon as feasible and return for a Follow-Up visit 4 weeks (-7 days /+2 days) after the last dose of study drug.
Targeted Physical Examination		X¢	х	х	x	x	x			A targeted physical examination will be conducted as needed, based on clinical judgement of the Investigator, to evaluate reported current or prior AEs, symptoms reported by the patient, or abnormal laboratory readouts.
Vital Signs	х	Xc	x	х	x	x	x	х	х	Includes temperature, pulse rate, respiratory rate, and blood pressure. Blood pressure and pulse measurements should be preceded by at least 5 minutes of rest for the patient in a quiet setting without distractions.
12-lead ECG	х	Xc	х	х	x	x	x	х	х	Participants will lie supine in a quiet setting without distractions for at least 10 minutes prior to 12-lead ECG collection.
Smoking status		Х					Х		Х	
AE Review		←						>		See Section 8.5 for additional details on AE and SAE reporting.

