For any THR- β agonist, a key safety concern is excess systemic thyroid hormone stimulation, which could include effects on the cardiovascular and skeletal systems such as increased heart rate, cardiac hypertrophy, muscle wasting, and reduced bone density, in addition to the other clinical signs or symptoms that are possible with hyper/hypothyroidism. THR- α is the predominant THR expressed in the heart and bone, and responsible for most of the unwanted cardiovascular and skeletal effects associated with thyroid hormone stimulation (Johansson 1998; Gloss 2001; Sinha 2019; Gorka 2013). As described previously, THR- β agonism in the liver has been implicated in lowering free T4 (prohormone) without changes in T3 (active hormone) or TSH, which may be attributed to peripheral thyroid hormone modulation (Taub 2013; Berry 1990).

Toxicology studies for TERN-501 suggest the possibility of peripheral and central thyroid hormone modulation with TERN-501 based on dose-dependent reduction of TSH in rodents, which was considered a non-adverse finding. In FIH Study TERN501-1009, however, thyroid axis test findings appeared consistent with peripheral thyroid hormone modulation, showing dose-dependent lowering of free T4 without changes in free T3 or TSH. No clinical signs or symptoms of hyper/hypothyroidism were reported as AEs at any dose level evaluated in the study. Extensive cardiovascular monitoring including frequent vital signs, 12-lead

electrocardiograms (ECGs), and cardiac biomarkers showed no clinically significant changes in those parameters. Overall, there was no evidence for central thyroid axis suppression or cardiac toxicity with TERN-501 administered at single doses up to 60 mg and repeat doses of up to 10 mg once daily for up to 14 days in the FIH study. Nonclinical studies for TERN-501 support lack of anticipated adverse cardiovascular effects at clinically relevant doses. Refer to the TERN-501 Investigator's Brochure for additional details.

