8.1.7. Cardiovascular Safety Monitoring

Cardiovascular safety will be monitored via vital signs (see Section 8.1.5) and 12-lead ECGs (see Section 8.1.6) along with clinical assessment of adverse events that may represent signs or symptoms of cardiac toxicity.

Signs and symptoms that may reflect cardiovascular toxicity include the following, with clinical significance to be determined by the Investigator:

- Vital signs changes including hypertension, hypotension, tachycardia, or bradycardia
- 12-lead ECG findings including tachycardia, bradycardia, atrial fibrillation or flutter, ventricular arrythmia, or QTc prolongation
- Clinical symptoms suggestive of cardiac ischemia or other cardiac dysfunction such as chest pain/pressure, palpitations, shortness of breath, or edema

Potential signs or symptoms consistent with cardiovascular toxicity should be carefully evaluated, with repeat of assessments (e.g., vital signs, ECG, laboratory values) to confirm findings and follow-up until resolution.

Signs or symptoms should be designated as AEs with CTCAE v5.0 severity determined per Appendix 6. Participant discontinuation of study drug criteria are outlined in Section 7.1.2.

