9.4.5. Safety Endpoints

In addition to the secondary endpoint of patient incidence of TEAEs, patient incidence of TEAEs will also be summarized by maximum intensity and study drug causality. Summaries of treatment-emergent SAEs will be summarized in the same manner as the secondary endpoint.

Vital signs and quantitative safety laboratory measurements will be summarized by treatment group and scheduled time points. Laboratory abnormalities will be graded according to NCI CTCAE Version 5.0, where applicable. The number and percentage of subjects experiencing treatment-emergent graded lab toxicities will be summarized by treatment group and toxicity grade.

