3.8. Visits

3.8.1. Windows

In data listings, the relative study day of all dates from first dose will be presented.

Scheduled visit assessments will be determined based on a two-step process using the parameters of exposure to study drug and scheduled visit assessment windows.

Step 1:

• The last dose date (maximum from dates of discontinuation form and exposure data) must be within 14 days, inclusive, of the last assessment of those within the treatment exposure period (12 weeks). If the last dose date is after or within 14 days inclusive of the Week 12 assessment there will be an assumption that all previous assessments were performed while under proper drug exposure. Any assessments performed greater than 14 days of the last dose date will be considered unscheduled irrespective of Table 4 mapping.

Step 2:

- Use Table 4 to initially map the appropriate assessment under consideration
- For multiple assessments mapped to the same scheduled visit interval, select the assessment date that is closest to the target day of the visit window in terms of absolute difference, irrespective of scheduled or unscheduled visit type. Any assessment not selected in the window is considered unscheduled.

In the event of a scheduled visit assessment tie AND the assessment was performed as an original scheduled assessment select this over an unscheduled; if both assessments are unscheduled or scheduled select the first assessment, then classify the other as unscheduled.

Final, Version 2.0, 26JULY2023

CONFIDENTIAL

Labcorp Drug Development Study: 000000231152 Protocol Reference: TERNCB-2002

Table 4 Treatment Period Visit Windows

Target Scheduled Visit	t Scheduled Visit Target Study Day ^a Analysis Window Study Day ^a		
	•	Low	High
Targeted physical examina	ation, vital signs, EC	CG, chemistry and hema	atology labs
Baseline	1	See Section 3.6.2	
Week 2	15	2	22
Week 4	29	23	36
Week 6	43	37	50
Week 8	57	51	70
Week 12	85	71	99
Thyroid axis testing	•		·
Baseline	1	See Section 3.6.2	
Week 2	15	2	29
Week 6	43	37	50
Week 12	85	71	99
Weight, MRI-PDFF, MRI	-cT1, and fibrosis b	iomarkers	·
Baseline	1	See Section 3.6.2	
Week 6	43	29	57
Week 12 ^b	85	71	99
Week 16	For all		
	parameters, use nominal visit as		
	recorded on CRF.		

a Study Day will be calculated from first dose of study drug. Visit windows defined by the low and high values are inclusive.

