8.5. Electrocardiograms

Summary statistics will be provided for heart rate, PR interval, QRS interval, QT interval, and QTcF at each visit. The investigator interpretation is collected as normal, abnormal not clinically significant (NCS), or abnormal clinically significant (CS). Patients whose interpretation shifts from normal to abnormal (CS or NCS) will be listed separately including description of the abnormality and any associated comments.

Categorical summaries will for baseline, worst post-baseline, and change from baseline for the following QTcF values will be presented:

- > 450 msec
- > 480 msec
- > 500 msec
- Change from baseline > 30 msec
- Change from baseline > 60 msec

CONFIDENTIAL

All ECG results will be presented in by-patient data listings. If applicable, cardiologist consult information will be presented in a separate by-patient data listing.

CONFIDENTIAL

9. Other Assessments

Other assessments will be provided in by-patient data listings only; no summary tables will be provided, including but not limited to the following:

- Eligibility details including unmet eligibility criteria
- Informed consent
- Randomization schema
- Physical examination collection information
- Serology
- Pregnancy testing
- FSH test
- Urine drug screen
- Alcohol test
- Urinalysis and Urine Microscopic Examination
- Coagulation
- Hemoglobin A1c
- Direct bilirubin
- Indirect bilirubin
- Laboratory reference ranges
- Cardiology consult
- Overdose
- Comments

Final, Version 2.0, 26JULY2023

CONFIDENTIAL

10. Changes to Protocol Planned Analyses

There were no changes from the protocol planned analyses.

CONFIDENTIAL

Statistical Analysis Plan CONFIDENTIAL Labcorp Drug Development Study: 000000231152 Protocol Reference: TERNCB-2002

11. Appendices

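### Blood pressure and heart rate are summarised only as observed values by visit, with no within-patient change from baseline and no specified baseline-adjusted difference from placebo

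*SAP*

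**What the plan says.** SAP 8.4 is the whole vital-signs analysis. It states: "Summary statistics will be provided for systolic and diastolic blood pressure, and heart rate for each visit". It adds that clinically significant abnormalities are reported as adverse events. It names no change from baseline, no threshold or shift table and no model.

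SAP 8.5 handles the second source of heart rate in the same way: "Summary statistics will be provided for heart rate, PR interval, QRS interval, QT interval, and QTcF at each visit". Numeric change from baseline is planned there only for QTcF categories. Shifts in the investigator's ECG reading from normal to abnormal are listed.

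Protocol 9.4.5 supplies the grouping: "Vital signs and quantitative safety laboratory measurements will be summarized by treatment group and scheduled time points". It does not mention change.

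Protocol 2.3, discussing excess systemic thyroid hormone stimulation as a concern for any THR-β agonist, refers to "effects on the cardiovascular and skeletal systems such as increased heart rate". Protocol 8.1.7 makes vital signs and 12-lead ECGs the tools for cardiovascular monitoring, together with clinical assessment of adverse events.

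**The concern.** A by-visit mean mixes the drug effect with whatever difference the arms had before dosing. With about 20 patients per arm and stable between-patient differences in resting heart rate, that starting difference can be as large as a moderate drug effect. It can hide a real rise or suggest one that is not there. The within-patient change removes the starting level, and its spread cannot be rebuilt from tables of visit means and SDs. Patients who leave also change who contributes to each row, so subtracting one row's mean from another's is only approximate.

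The SAP already uses change from baseline for most other quantitative safety measures, and for two groups of them it goes on to modelled differences between arms. No reason is given for leaving out the two cardiovascular measures. At stake is how clearly a 12-week safety signal in patients can be read. The primary and secondary efficacy results are not affected.

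**Working it through.** **1. Treatment of quantitative safety measures in the SAP**

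| Measure | SAP section | Change from baseline | Modelled difference between arms, 95% CI |
|---|---|---|---|
| Chemistry, hematology, urinalysis | 8.3 | Yes, also percent | No |
| Thyroid axis | 8.3.2 | Yes | Yes |
| Sex hormones | 8.3.3 | Yes | Yes |
| Bone turnover markers | 8.3.4 | Yes | No |
| Blood pressure, heart rate (vital signs) | 8.4 | No | No |
| ECG heart rate | 8.5 | No (QTcF categories only) | No |

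**2. Is a baseline available?** Yes. The Schedule of Activities (Protocol 1.3) marks vital signs at Screening and pre-dose at Week 0, and SAP Table 4 has a Baseline row for vital signs and ECG. Protocol 9.4.1 gives a default for non-laboratory data: the latest value before first dose. SAP 3.8.2 names weight, BMI and ECG parameters but not vital signs.

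**3. Inputs for the size.** Patients per arm: 20 (SAP 2.3). The SD of heart rate and its baseline-to-visit correlation r are not in the documents. Assumed for illustration: SD 8-12 bpm, the same at baseline and follow-up, and r from 0.3 to 0.8. The plan states no figure of its own for these measures, so there is none to reproduce.

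**4. Chance baseline difference between two arms.** Standard error = SD × √(2/20) = SD × 0.316.
- SD 8: 2.53 bpm
- SD 10: 3.16 bpm
- SD 12: 3.79 bpm

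**5. 95% half-width for active minus placebo.** The t quantile on 38 df is 2.024.
- Observed values: 2.024 × SD × √(2/20). SD 10 gives 2.024 × 3.162 = 6.4 bpm; SD 8 and SD 12 give 5.1 and 7.7.
- Change from baseline: multiply by √(2(1 − r)).
- ANCOVA on baseline: multiply by √(1 − r²).

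At SD 10 (bpm):

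| r | Observed values | Change score | ANCOVA |
|---|---|---|---|
| 0.3 | 6.4 | 7.6 | 6.1 |
| 0.5 | 6.4 | 6.4 | 5.5 |
| 0.7 | 6.4 | 5.0 | 4.6 |
| 0.8 | 6.4 | 4.0 | 3.8 |

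The change score is more precise than observed values only when 2(1 − r) < 1, that is r > 0.5. ANCOVA is more precise at every correlation tried, but at r = 0.3 the gain is small: √0.91 = 0.954, about 5%.

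**6. Number of intervals a model would produce.** Two measures × 6 active arms × 6 post-baseline visits (Weeks 2, 4, 6, 8, 12, 16) = 72. With no true effects, 72 × 0.05 = 3.6 would be expected to exclude zero. At Week 12 only, with one heart-rate source: 2 × 6 = 12, and 12 × 0.05 = 0.6.

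**The case against.** The strongest reply is that the plan already covers the ground for a descriptive phase 2a safety analysis.

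- **Baseline.** A reader might infer that baseline is ignored. It is not. Table 4 maps a Baseline visit, so baseline means and SDs by arm can appear as a row, an imbalance can be seen there, and individual data are listed. What is missing is narrower: the within-patient change and its spread.
- **Placebo.** A reader might infer that there is no comparison with placebo. The tables are by treatment group with placebo as the first column, and SAP 3.1 speaks in general terms of two-sided 95% intervals for comparing groups. This stands as far as it goes, but 8.4 and 8.5 name no comparison or model, so nothing commits the sponsor to a baseline-adjusted one.
- **Other capture.** Protocol 8.1.7 has possible cardiovascular signs evaluated, repeated and recorded as graded adverse events, and adverse-event incidence is a secondary endpoint. So cardiovascular safety does not rest on visit means alone. These routes depend on the investigator's judgement for each patient, though, and would not show a moderate shift in an arm's mean.
- **Prior data.** Protocol 2.3 attributes most cardiac effects to THR-α and reports no clinically significant cardiovascular changes at up to 10 mg daily for 14 days, above the 6 mg maximum here. The text therefore does not make heart rate the single key measure. Those data came from healthy subjects in multiple-dose cohorts of 8 randomised 3:1; this trial runs 12 weeks in patients.
- **Remedy.** Routine laboratory tests and bone markers get descriptive change only, so a model for vital signs goes beyond parity with them, and a model at every visit would create many unadjusted intervals. This stands and limits the model to Week 12.
- **Shells.** The table shells are outside the documents and may contain change columns. The SAP text does not require them.

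**Conclusion.** The point holds in a limited form. SAP 8.4 and 8.5 specify only observed values by visit for blood pressure and heart rate. Within-patient change and a baseline-adjusted difference from placebo are not specified, although a baseline is collected and most other quantitative safety measures get change from baseline.

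The size is modest and rests on assumptions. With 20 per arm and an assumed SD of 8-12 bpm, a chance baseline difference of 2.5-3.8 bpm (one standard error) carries into by-visit comparisons to the extent that heart rate tracks within a patient. At SD 10, ANCOVA would shorten the 95% half-width from 6.4 bpm to between 6.1 and 3.8 bpm, depending on a correlation that the documents do not give. A reader might infer that adding change columns alone buys precision. It does so only if r exceeds 0.5; otherwise their value is descriptive. Nor do the documents show that a particular drug effect would be missed, because they define no effect size of interest for heart rate. This is a worthwhile improvement, not a flaw that threatens the trial's conclusions.

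**What to change.** - In SAP 8.4 and 8.5, add descriptive change from baseline by visit and treatment group for systolic pressure, diastolic pressure and heart rate (vital signs and ECG).
- For heart rate and systolic pressure, add the Section 7.7 ANCOVA difference from placebo with its 95% interval at Week 12 only, labelled descriptive and unadjusted for multiplicity. State which heart-rate source the model uses.
- In SAP 3.8.2, name vital signs in the baseline definition as the last value before first dose, which matches the Protocol 9.4.1 default.

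Cost: a few extra table columns and, with one heart-rate source, 12 unadjusted intervals. No new data are needed.
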